## 6.2 Sample Size Considerations

Our primary comparison of interest is the effect on targeting of ACTs, offering a combination of outlet incentives for testing (provider-directed intervention), and ACT subsidies for malaria test-positive clients (client-directed intervention) relative to a control arm where outlets are able to offer malaria testing but neither the provider nor the client receives any extrinsic incentive to test (Arm 4 versus Arm 1). In order to evaluate whether the client-directed intervention and the provider-directed intervention do, in fact, have a synergistic effect on the outcome, we also have two secondary comparisons of interest: (1) the combined provider- and client-directed interventions relative to the provider-directed intervention alone (Arm 4 versus Arm 2) and (2) the combined provider- and client- directed interventions relative to the client-directed intervention alone (Arm 4 versus Arm 3).

We calculated power based on a cluster randomized two-sample two-tailed t-test for the comparison of two proportions using standard formulae [28]. We calculated power for differences in our primary outcome for each of the three comparisons of interest noted above. To ensure that our overall two-tailed Type I error (alpha) is 5%, we fixed the alpha level at 1.667% (i.e. 5%/3) for each of the 3 comparisons of interest, using the conservative Bonferroni correction [29]. We estimated the intra-class correlation coefficients (ICCs) for the primary outcome to be 0.006 in Nigeria.

**Table 2:** Assumptions in Nigeria for sample size calculation for Aim 2

|   | Expected Percentage of ACTs taken by Clients Testing Positive for Malaria | Power (# of exit interviews per arm) | Nigeria (2040) |
|---|---|--------------------------------------|----------------|
| Arm 1: Control Arm
(RDT only, no incentives)  | 15%   | >99%                                 |                |
| Arm 2: Provider-Directed Intervention (Shopkeeper incentives for malaria testing)        | 17%   | >99%                                 |                |
| Arm 3: Client-Directed Intervention (ACT subsidy to client conditional on positive test) | 26%   | 89%                                  |                |
| Arm 4: Combined Provider- and Client-Directed Interventions                              | 40%   | Ref. Group                           |                |

Our primary outcome—the proportion of ACTs that are taken by malaria test-positive clients—is a combination of the proportion of individuals who get tested for malaria and the proportion of tested individuals who treat according to the test result. We anticipate that 15% of ACTs will be purchased by clients with a positive test in the control arm (with 85% of ACTs purchased by those without a test or with a negative test). Moreover, we hypothesize that both the provider-directed intervention, and the client directed intervention on their own will only increase testing marginally (on the order of ~5 percentage

points), but that among those who do test, the client-directed intervention alone will substantially increase the proportion of malaria-positive individuals who take an ACT [30]. As a result, we expect that the provider-directed intervention (Arm 2) will have only a small effect on ACT targeting, that the client-directed intervention (Arm 3) will have a somewhat larger effect, but that the largest effect will come from combining the two interventions (Arm 4) (i.e., we assume a statistical interaction). With a sample of 170 exit interviews per outlet (48 outlets in Nigeria), we will have >90% power to detect a minimum difference between Arms 1 and 4 in the primary outcome of 25 percentage points. We will also have >89% power to detect a minimum difference of 16 percentage points for the main secondary comparison of interest (testing uptake).

Due to the nature of the interventions, it is not possible to blind participants and the implementation team to the allocation received. Data collectors will be blinded throughout collection and study statisticians will be blinded during the analysis phase.

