**In order to align both the provider and customer incentives towards testing and targeting, the provider must be willing to perform the test and sell the appropriate medicine and, at the same time, the customer must be motivated to purchase the test and adhere to the results. We hypothesize that offering ACT subsidies for the client (conditional on a positive test), and incentives to the provider to offer malaria testing, will each, on their own, have a very modest impact on uptake of testing and targeting of ACTs in the retail sector. We further hypothesize that when combined, they will have a synergistic effect on RDT testing and ACT targeting.** However, it is important to estimate the effect of each intervention separately and in combination in order to provide cogent evidence to support joint implementation. We will test the combination of subsidies for ACTs and RDTs (selected from Aim 1) paired with a provider-directed testing incentive in a four-arm cluster-randomized controlled trial to evaluate their impact on the proportion of ACTs sold to individuals with parasitologically-confirmed malaria among those seeking care in the retail sector.

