### 3 STUDY DESIGN

This will be a four-arm cluster-randomized trial based on an underlying 2x2 factorial design. A random sample of 48 PPMVs (clusters) will be selected from a complete sampling frame of all eligible outlets and subsequently randomly assigned in a 1:1:1:1 ratio to each of the 4 arms (see Table 2).

All clusters (Arm 1-4) will have access to RDTs at the wholesale price that enables the outlet to charge the desired retail price. The study will pre-specify the retail price so that it is consistent across all the arms and pharmacies and will work with in-country wholesalers to provide RDTs at the appropriate price to all participating outlets. In addition, all outlets will be trained on a mobile reporting app and asked to use it to record RDT and ACT sales and to facilitate payment of financial incentives. The four treatment arms are as follows:

- (1) Control (Arm 1): No price subsidy or incentive. RDTs are made available at wholesale price to the retail outlet.
- (2) Provider-directed intervention (Arm 2): Retail outlet in this arm receives a small incentive to perform an RDT for suspected malaria cases
- (3) Client-directed conditional ACT subsidy (Arm 3): Clients visiting outlets in this arm will receive an ACT discount *if* they purchase a malaria test and have a positive test result.
- (4) Combined interventions (Arm 4): Retail outlets in this arm receive an incentive to test for malaria and clients visiting these outlets receive an ACT discount conditional on a malaria positive test (i.e. this arm is a combination of the provider-directed and client-directed interventions that are offered in Arm 2 and Arm 3).

Our four-arm study design will allow us to measure the effect of joint incentives to the provider and consumer, relative to no incentives and relative to either incentive alone.

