Our sample size estimates correspond to a total of 8160 exit interviews with clients. Since not everyone interviewed will have purchased an ACT, our estimates account for the fact that only a subset will enter into our analysis for the primary outcome.

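### The two comparisons named to evaluate synergy (Arm 4 vs 2, Arm 4 vs 3) show added value over one incentive, not interaction; no interaction contrast or scale is prespecified

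*Combined protocol and SAP*

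**What the plan says.** Section 1.1 states the hypothesis: "We further hypothesize that when combined, they will have a synergistic effect on RDT testing and ACT targeting". Section 6.2 gives Arm 4 vs Arm 1 as the primary comparison. It then adds Arm 4 vs Arm 2 and Arm 4 vs Arm 3, and gives their purpose as "In order to evaluate whether the client-directed intervention and the provider-directed intervention do, in fact, have a synergistic effect on the outcome". The three comparisons share a Bonferroni-corrected 5%. Later in 6.2 the expected pattern is described in brackets: "i.e., we assume a statistical interaction".

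Section 3 puts the aim differently: the effect of joint incentives "relative to no incentives and relative to either incentive alone". Section 6.4 fits a GEE model with indicators for Arms 1-3 and Arm 4 as reference. It uses a log link for risk ratios and an identity link for risk differences. No section names a contrast of all four arms, a scale for synergy, or its power.

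**The concern.** Synergy means that the combination does more than the two separate effects predict, and that prediction needs the control arm. Arm 4 above Arm 2 shows that adding the client subsidy helps. Arm 4 above Arm 3 shows that adding the provider incentive helps. Two incentives that simply add up pass both tests if each effect is large enough.

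Two significant comparisons could therefore be reported as synergy without evidence of interaction. The answer also depends on scale, and a scale chosen after the results are known is open to challenge. Section 1.1 claims synergy for RDT testing as well as ACT targeting, so the gap covers both outcomes.

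**Working it through.** **Inputs.** From Section 6.2 and Table 2: expected rates 15%, 17%, 26% and 40% in Arms 1-4; 12 outlets per arm (48/4); 170 interviews per outlet; ICC 0.006; two-sided alpha 5%/3 = 1.667%; stated power 89% for Arm 4 vs 3 and >99% for Arm 4 vs 1 and vs 2. Not stated: how many of the 170 buy an ACT. Section 6.3 says only that "our estimates account for the fact that only a subset will enter into our analysis for the primary outcome".

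**Step 1: the plan's 89%.** With m buyers per outlet, the variance of an arm's rate is p(1-p)[1+(m-1)0.006]/(12m). With all 170 counted, power exceeds 99.9%. Solving for 89% gives m = 28 (normal; 16% of 170) or m = 33 (t, 22 df; 19%). For m = 28 the design effect is 1.162 and n is 336 per arm. The variances (×10⁻⁴) for Arms 1-4 are 4.41, 4.88, 6.65 and 8.30. The SE for Arm 4 vs 3 is √(14.95×10⁻⁴) = 0.0387, and 0.14/0.0387 = 3.62 against a critical value of 2.394, giving 89%. Both values of m also give >99% for the other two comparisons, so Table 2 is consistent with 28-33 buyers per outlet. That range is assumed for ACT targeting below.

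**Step 2: the interaction in Table 2.**
- Difference scale: 40 - 26 - 17 + 15 = +12 points. No interaction would put Arm 4 at 17 + 26 - 15 = 28%.
- Ratio scale: (0.40×0.15)/(0.17×0.26) = 1.36. No interaction would put Arm 4 at 0.17×0.26/0.15 = 29.5%.

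**Step 3: precision and power of the interaction** (t, 44 df, critical value 2.015). The SE is the root of the sum of the four variances. On the log scale each term is (1-p)/p × design effect/n.

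| | m = 28 | m = 33 |
|---|---|---|
| Difference: SE | 0.0492 | 0.0459 |
| Expected 95% CI, points | +2.1 to +21.9 | +2.7 to +21.3 |
| Power at 5% | 66% | 72% |
| Log ratio of RRs: SE | 0.227 | 0.212 |
| Expected 95% CI, ratio | 0.86 to 2.14 | 0.89 to 2.08 |
| Power at 5% | 26% | 29% |

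**Step 4: how often both comparisons are significant** (simulated arm rates; ranges span m = 28-33 and t or normal critical values).

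| True rates, Arms 1-4 (%) | Interaction | Both significant |
|---|---|---|
| 15/17/26/28 | zero (difference) | 2-3.5% |
| 15/17/26/29.5 | zero (ratio) | 5-8% |
| 15/17/26/40 (Table 2) | +12 points | 85-93% |
| 15/22/26/33 (hypothetical) | zero (difference) | 21-32% |
| 15/27.5/27.5/40 (hypothetical) | zero (difference) | 60-77% |

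Under Table 2, both are significant while the interaction CI includes no effect in 19-24% of all trials (difference) and 60-65% (ratio).

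**Step 5: one concrete result.** Take m = 28, with Arms 1-3 observed as planned and Arm 4 at 36%. The Arm 4 variance is 0.2304×1.162/336 = 7.97×10⁻⁴. Arm 4 vs 3 gives 0.10/√(14.62×10⁻⁴) = 2.61, above the t critical value 2.591. Arm 4 vs 2 gives 0.19/√(12.85×10⁻⁴) = 5.30. Both are significant. The interaction is 36 - 26 - 17 + 15 = +8 points, with SE √(23.91×10⁻⁴) = 0.0489 and 95% CI -1.9 to +17.9. Depending on m and the critical value, this occurs for an observed Arm 4 from about 35-36% up to 37-38%.

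**Step 6: testing uptake (illustrative).** Section 6.2 claims >89% "power to detect a minimum difference of 16 percentage points for the main secondary comparison of interest (testing uptake", but gives no control rate, ICC or pair of arms. It expects about +5 points from each incentive alone. If the 16 points is Arm 4 vs 1, the interaction is 16 - 5 - 5 = +6 points. With the SE set so that 16 points has 89% power, interaction power is about 14-18% and the CI half-width 12-14 points. Both comparisons are significant in about 1.5-4.5% of trials under additivity. These ranges use control rates of 10-50%, 100-170 clients per outlet, and alpha 1.667% or 5%.

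**The case against.** The comparisons do what Section 3 asks. At the planned single-arm rates a false signal is rare on the difference scale (2-3.5%), so there the pairwise rule is a fairly conservative screen. The high false-signal figures need a provider effect of 7 or 12.5 points, where Table 2 plans 2. Under Table 2 the interaction is real, so claiming it would be correct, and the 19-24% reflects imprecision rather than error. The three-indicator model already contains the interaction on both scales. The testing-uptake figures rest on inputs the plan does not state, and 6.2 powers its comparisons on the primary outcome.

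All of this limits the size of the problem, and the hypothetical cases should carry no weight for severity. It does not rescue the rule. The low false-signal rate belongs to the planned rates and is not a property of the comparisons. A true interaction does not mean that a given trial's data have shown it. A loose reading of synergy is hard to sustain when 6.2 itself speaks of a statistical interaction and Section 3 describes an underlying 2x2 factorial design. That a contrast can be derived does not make it, or its scale, prespecified.

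**Conclusion.** The concern holds and should be fixed. The rule in 6.2 does not answer the question assigned to it. The bracketed planning assumption is itself correct for Table 2, and the primary comparison and the added-value question are sound.

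The practical consequence is an overstated claim. A direct interaction estimate would be much less precise than the pairwise power of 89% to >99% suggests, particularly on the ratio scale. The logical point needs no assumption. The ACT-targeting sizes rest on 28-33 buyers per outlet, equal cluster sizes and no covariate adjustment. The testing-uptake sizes are illustrative only.

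**What to change.** In 6.2 and 6.4, prespecify the interaction contrast from the planned GEE model for ACT targeting and for RDT testing uptake. With Arm 4 as reference it is b1 - b2 - b3. Under the identity link this equals p4 - p3 - p2 + p1; under the log link it is ln[p4·p1/(p2·p3)]. Name one scale as primary, for example the risk difference because Table 2 is in percentage points, and report the other as well. Give the estimate and 95% CI with the small-sample correction already planned. Label it supportive estimation, with no significance claim, outside the three-comparison family, so that the overall 5% stands. State the assumed ACT-buyer share and the lower power. Relabel Arm 4 vs 2 and Arm 4 vs 3 as added value over one incentive alone.

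If a formal claim on ACT targeting is wanted, make it a fourth family member at 5%/4 = 1.25%. Arm 4 vs 3 then falls from 89% to about 86-87%, and the interaction test has 44-51% power (difference) or 12-14% (ratio).

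If no interaction claim is intended, reword the purpose in 6.2 and the hypothesis in 1.1 as superiority of the combination over each incentive alone. The planning assumption can stay, but no synergy claim can then be made.

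The cost is SAP wording and one linear contrast per outcome, with no change to design or data. The low power for synergy becomes visible, most of all for testing uptake.

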## 6.4 Analysis Plan

We will analyze client-level outcomes by fitting a modified Poisson regression model [31, 32] with log link to estimate risk ratios (RRs) and identity link to estimate risk differences. Such an approach assumes a Poisson distribution for the binary outcome and then 'fixes' the estimated standard errors to correct for model misspecification.

To account for clustering by outlet we will use a generalized estimating equations (GEE) [33, 34] approach with exchangeable working covariance matrix and robust standard errors (to correct for model misspecification due to specifying a Poisson distribution). The outcome will be regressed on three binary indicators for each of the treatment arms 1-3, with treatment arm 4 (the combined interventions) serving as the reference group. The model will also include a vector of potential confounder variables (e.g., age, gender, education, household distance to closest health facility, study quarter) to account for possible imbalances between study arms. All analyses will be based on the intention-to-treat principle whereby all clients will be included in the analysis irrespective of whether they complied with the intervention in the outlet at which they sought care (e.g. even if they did not use the ACT subsidy if they tested positive in an outlet in Arms 3 and 4 that received the client-directed intervention).

Given that the literature indicates that when there are fewer than 40 clusters in a cRCT, small sample correction methods should be used to ensure that standard error estimates are correctly estimated when using GEE to analyze binary outcomes, and given that the size of the cRCTs in each country are close to this cut-off, we plan to adopt the use of the Kauerman-Carroll correction to avoid any possible problems [35, 36]. We will compare secondary outcomes using the same modeling approach.

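### Equal Bonferroni split across three comparisons costs power on Arm 4 versus Arm 3; Holm keeps the same 5% familywise error and lifts that power from 89% to about 95–96%

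*Combined protocol and SAP*

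**What the plan says.** Section 6.2 names Arm 4 versus Arm 1 as the main comparison on the primary outcome and adds, for the question of synergy, "we also have two secondary comparisons of interest": Arm 4 versus Arm 2 and Arm 4 versus Arm 3. To hold the overall two-sided error at 5%, it states "we fixed the alpha level at 1.667% (i.e. 5%/3) for each of the 3 comparisons of interest, using the conservative Bonferroni correction".

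Table 2 assumes that 15%, 17%, 26% and 40% of ACTs go to test-positive clients in Arms 1 to 4. It reports power of >99%, >99% and 89% for Arm 4 against Arms 1, 2 and 3.

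Section 6.4 describes the regression model, with Arm 4 as the reference group. It gives no significance level, multiplicity procedure or testing order for the three contrasts. Its only remark on further testing is "We will compare secondary outcomes using the same modeling approach", which concerns secondary outcomes and not the three comparisons.

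**The concern.** A single-step Bonferroni split keeps each test at 1.667% whatever the other two show. Here two of the three tests are expected to succeed almost with certainty, so their share of alpha goes unused, and the third test bears the cost.

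That third test, Arm 4 versus Arm 3, decides whether paying the provider adds anything to the client subsidy. A claim that the combination beats each component alone needs both Arm 4 versus Arm 2 and Arm 4 versus Arm 3 to succeed, and the latter is the weaker of the two. Section 1.1 treats separate and joint estimates as necessary evidence for implementing the two interventions together, so a missed difference here would weaken one of the trial's main messages.

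**Working it through.** **Inputs**
- Two-sided familywise alpha 5%, three comparisons (Section 6.2): 0.05/3 = 0.01667, as stated.
- Rates and power from Table 2, as above.
- Power method (Section 6.2): "We calculated power based on a cluster randomized two-sample two-tailed t-test for the comparison of two proportions".
- ICC (Section 6.2): "for the primary outcome to be 0.006 in Nigeria".
- Size (Section 6.2): "With a sample of 170 exit interviews per outlet (48 outlets in Nigeria". With equal allocation (Section 3) that is 48/4 = 12 outlets and 12 × 170 = 2040 interviews per arm.
- ACT buyers per outlet, m: not stated. Section 6.3 says only that a subset of interviewees enters the primary analysis.

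**Step 1. The plan's 89%.** Take the design effect as 1 + (m − 1) × 0.006 and the standard error as √{[0.26 × 0.74 + 0.40 × 0.60] × design effect / (12m)}.
- With m = 170, power for Arm 4 versus Arm 3 at 1.667% is above 99.9%, so the 89% must rest on a smaller m.
- Solving for 89% gives m of about 28 (normal), 33 (t, 22 df) or 34 (Hayes–Moulton formula), which is 17% to 20% of interviewees.
- At those sizes Arm 4 versus Arms 1 and 2 have power above 99.9%, in line with Table 2.

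The 89% therefore cannot be rebuilt directly, but nothing shows it to be wrong. The next step takes it as given and does not need m.

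**Step 2. Same comparison at 5%.**
- Normal: noncentrality = z(0.89) + z(1 − 0.01667/2) = 1.2265 + 2.3940 = 3.6205. Power at 5% = Φ(3.6205 − 1.9600) = **95.2%**.
- Noncentral t, 22 df: the noncentrality giving 89% at 1.667% is 3.878. Power at 5% = **95.9%**. With 44 df it is 95.6%.
- If the 89% is rounded (88.5% to 89.5%), the range across these methods is 94.9% to 96.2%.

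**Step 3. Does Holm deliver the 5% level?** Holm compares the ordered p-values with 1.667%, 2.5% and 5%. It was simulated on three tests sharing Arm 4, with Table 2 rates and 12 outlets per arm (200,000 trials each).

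| Reference | m | Bonferroni, 4 v 3 | Holm, 4 v 3 |
|---|---|---|---|
| t, 22 df | 33.0 | 89.0% | 96.0% |
| normal | 28.5 | 89.4% | 95.4% |

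With exactly 28 buyers per outlet and the t reference, a separate simulation gave 83.5% and 93.0%.

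**Step 4. Familywise error of Holm (simulated).**
- All three null: 4.5%, the same as Bonferroni.
- Only Arm 4 versus Arm 3 null: 4.9% to 5.0% (Bonferroni 1.7%).
- Arm 4 versus Arms 2 and 3 null: 4.7% to 4.8%.

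**Step 5. What the gain is worth.** Reaching 95.2% while staying at 1.667% would need noncentrality 1.6605 + 2.3940 = 4.0545. The ratio (4.0545/3.6205)² = 1.25 means about 25% more effective sample for this comparison. Holm needs no extra interviews.

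**Step 6. Sensitivity.**
- If Arm 2 were as high as 26%, Holm would still give 94.6% to 94.9% for Arm 4 versus Arm 3.
- As assumptions about m (normal reference): 20 buyers per outlet gives 77% under Bonferroni and 88% under Holm; 15 gives 64% and 78%.
- In the other direction (t, 22 df): a 25% buyer share (m = 42.5) gives 94.7% at 1.667% and 98.4% at 5%; a 40% share gives 99.2% and 99.8%.

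**The case against.** Bonferroni is not an error. It controls the error rate as intended, the plan itself calls it conservative, and the reference it cites is titled as a comparison of Bonferroni with Holm. All of that stands: the point concerns lost efficiency, not validity.

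The 1.667% appears only in the sample-size section, so it may describe sizing rather than the final tests. That is a fair reading. It also means the plan states no rule for the final tests, and a reader would assume 1.667%.

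Arm 4 versus Arm 3 is labelled secondary and already has 89% power, and the main comparison gains nothing. This is true, but it limits the importance of the point without removing it.

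A fixed-sequence or gatekeeping procedure would follow the plan's ranking and could also test Arm 4 versus Arm 3 at 5%. That is a legitimate alternative. Holm needs no pre-set order and never rejects less than Bonferroni.

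The size of the gain depends on the unstated buyer share. If that share is well above 17% to 20%, power is already high and the gain is small; if it is below, the gain is larger. The planned analysis is also an adjusted GEE with a small-sample correction, not the t-test used for power. Both caveats stand.

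Finally, intervals will not always agree with Holm. A 98.33% interval can include the null when Holm rejects, and an unadjusted 95% interval can exclude it when Holm does not. This is a real but small cost.

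**Conclusion.** The concern holds. Under the plan's own Table 2, replacing single-step Bonferroni with Holm raises power for Arm 4 versus Arm 3 from 89% to about 95–96%. The type II error falls by more than half, from 11% to between 4% and 5%, with familywise error still at most 5% and no loss on any other test. The figure rests on Table 2's rates and its 89%, which is taken as given because the share of ACT buyers is not stated. The present plan is valid, so this is a worthwhile, cheap improvement and not a correction of an invalid analysis.

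**What to change.** - In Section 6.2, replace the fixed 1.667% per comparison with Holm's step-down procedure at overall two-sided 5% for the three primary-outcome comparisons. Restate the Arm 4 versus Arm 3 power as about 95%, and give the assumed number of ACT buyers per outlet so that the figure can be checked.
- In Section 6.4, name the same procedure, report Holm-adjusted p-values, and say whether the risk-ratio or the risk-difference model supplies them, since both are fitted.
- State the interval convention in advance: unadjusted 95% intervals, or 98.33% intervals if simultaneous coverage is wanted. Add that either may occasionally disagree with the Holm decision.

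The cost is wording only, with no change to sample size, conduct or model. It should be settled before the statisticians are unblinded.

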### Secondary:

- The major secondary outcome is the proportion of suspected malaria cases that are tested with an RDT at the outlet. This outcome will allow us to determine whether the conditional subsidy can drive demand for testing.
- Other secondary outcomes will measure 1) adherence to the RDT result among all those tested at the outlet, 2) proportion of all suspected malaria cases that are managed appropriately (tested for malaria, and use ACT following a positive test or do not purchase an ACT after a negative test), and 3) ACT use by untested clients.

For questions regarding this protocol, contact *[name]* at the Clinton Health Access Initiative (CHAI).

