## 6 STATISTICAL CONSIDERATIONS

### 6.1 Study Outcome Measures

The primary outcome measure is the proportion of selected ACTs that are sold to individuals with a positive malaria diagnostic test defined as anyone who is tested at the outlet and receives a positive test result or is referred from a health facility or diagnostic lab with a documented positive test result.

$$\frac{\# \text{ people who tested positive and purchased ACT}}{\# \text{ people who purchased ACT}}$$

Among secondary outcomes, behavior will be measured for individuals who were tested at the outlet. Untested clients are those who chose not to be tested and did not come with a test result from another facility. The major secondary outcome is the proportion of suspected malaria cases that are tested. This outcome will allow us to determine whether the conditional subsidy can drive demand for testing. Note that “untested people” here refers specifically to individuals that present at the shop without a referral but decline to be tested.

$$\frac{\# \text{ people who were tested with an RDT}}{\# \text{ people who were tested with an RDT} + \# \text{ untested people who purchased an antimalarial}}$$

Other secondary outcomes will measure 1) adherence to the RDT result among all those tested at the outlet, 2) proportion of all suspected malaria cases that are managed appropriately (tested for malaria, and use ACT following a positive test or do not purchase an ACT after a negative test), and 3) ACT use by untested clients.

- Secondary outcome 2: Adherence to the RDT result among all those tested in the shop

$$\frac{\# \text{ people who tested positive and purchased ACT} + \# \text{ people tested negative and did not purchase any AM}}{\# \text{ people who were tested with an RDT}}$$

For those who are negative, if they buy any antimalarial (AM), including monotherapies and older therapies, they are not adhering to test result.

- Secondary outcome 3: Proportion of all suspected malaria cases that are managed appropriately in the shop

$$\frac{\# \text{ people who tested positive and purchased ACT} + \# \text{ people tested negative and did not purchase any AM}}{\# \text{ people who were tested with an RDT} + \# \text{ untested people who purchased an antimalarial}}$$

“Untested people” here refers specifically to individuals that present at the shop without a referral but decline to be tested

- Secondary outcome 4: ACT use among untested clients

---

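### Does the >89% power for 16 points in testing uptake contradict the rest of section 6.2?

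*Combined protocol and SAP*

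**What the plan says.** Section 6.2 names Arm 4 versus Arm 1 as the primary comparison and adds "we also have two secondary comparisons of interest": Arm 4 versus Arm 2 and Arm 4 versus Arm 3. On the power calculation it says "We calculated power for differences in our primary outcome for each of the three comparisons of interest noted above". Alpha is 5%/3 = 1.667% for each of the three, and "We estimated the intra-class correlation coefficients (ICCs) for the primary outcome to be 0.006 in Nigeria".

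Table 2 gives expected values of the primary outcome of 15%, 17%, 26% and 40% for Arms 1 to 4. Power against Arm 4 is >99%, >99% and 89% for Arms 1, 2 and 3.

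Two sentences below the table summarise power. One is for the primary outcome: "we will have >90% power to detect a minimum difference between Arms 1 and 4 in the primary outcome of 25 percentage points". The next is the sentence at issue: "We will also have >89% power to detect a minimum difference of 16 percentage points for the main secondary comparison of interest (testing uptake".

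The Protocol Summary says "The major secondary outcome is the proportion of suspected malaria cases that are tested with an RDT at the outlet", and section 6.1 agrees: "The major secondary outcome is the proportion of suspected malaria cases that are tested". Section 6.3 adds that "our estimates account for the fact that only a subset will enter into our analysis for the primary outcome".

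**The concern.** Three things make the sentence look like an error.

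- It calls testing uptake a comparison, although the section has just used that word for contrasts between arms. It names no arm pair.
- The only other 89% in the section is the Arm 3 row of Table 2. That row concerns ACT targeting, and its gap is 14 points. The sentence could be a garbled copy of the row, with both the outcome and the difference changed.
- If it is a separate calculation for uptake, no testing rates, arm pair, denominator, ICC or alpha are given for it. The only testing effect mentioned is about 5 points for each intervention alone. With 170 clients per outlet and an ICC of 0.006, the smallest uptake difference detectable with 89% power is far below 16 points.

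The preceding sentence may seem to have a similar fault. It calls 25 points a minimum for >90% power, while Table 2 already shows >99% at 23 points.

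At stake is whether a reader can trust the plan's only power statement for its major secondary outcome.

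**Working it through.** **Inputs from the plan (sections 6.2 and 6.3).** 48 outlets in four equal arms, so K = 12 per arm; 170 interviews per outlet; two-sided alpha 0.05/3; ICC 0.006 for the primary outcome.

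**Inputs assumed.** The number m of analysable clients per outlet, the uptake baseline (10% to 60%), and the uptake ICC (0.006 borrowed at first, then varied).

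**Formulae.** Design effect = 1 + (m − 1) × ICC. Effective n per arm = 12m / design effect. SE = √[(p₁q₁ + p₂q₂) / effective n]. Power comes from a noncentral t with 2 × 12 − 2 = 22 df (critical value 2.591).

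**Step 1: reproduce Table 2.** The gaps from Arm 4 are 40 − 15 = 25, 40 − 17 = 23 and 40 − 26 = 14 points. The share of clients who buy an ACT is not stated, so I solve for m.

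- For 26% v 40%, m = 33 gives design effect 1 + 32 × 0.006 = 1.192, effective n = 396/1.192 = 332, SE = √[(0.1924 + 0.2400)/332] = 0.0361 and 0.14/0.0361 = 3.88. Power is 89.0%.
- This needs 33/170 = 19% of clients to buy an ACT. The normal approximation needs m = 28, or 16.5%.
- At m = 33, Arm 4 v 1 and Arm 4 v 2 both exceed 99.9%.

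Table 2 is therefore coherent, with a subset of clients entering the primary analysis as section 6.3 says.

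**Step 2: could the sentence be the Arm 3 row?** At m = 33, 16 points on the primary outcome has 96.3% power (24% v 40%) or 95.8% (26% v 42%). So 16 points is not the 89% difference there. Only the figure 89 is shared; outcome and difference both differ. A copying slip is possible but is a guess.

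**Step 3: the sentence read as it labels itself, on uptake.** At ICC 0.006, baselines 10% to 60%:

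| Analysable clients per outlet | Power for 16 points | Smallest difference with 89% power | Uptake ICC at which 16 points has 89% power |
|---|---|---|---|
| 170 | >99.9% | 5.8 to 8.6 points | 0.036 to 0.067 |
| 85 | >99.9% | 7.2 to 10.5 points | 0.031 to 0.061 |
| 33 | 93.4% to 99.7% | 10.7 to 14.9 points | 0.012 to 0.043 |

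The claim of more than 89% is met in every row. Power falls to 89% at ICC 0.006 only when m is between 15 (10% v 26%) and 28 (42% v 58%).

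The ICC that would make 16 points the exact 89% minimum depends on m. It is 6 to 11 times 0.006 at 170 per outlet (0.036/0.006 and 0.067/0.006), but 2 to 7 times at 33 (0.012/0.006 and 0.043/0.006). No single multiple can be read from the plan.

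**Step 4: the 25-point sentence.** 25 points is exactly the Arm 4 v Arm 1 gap in Table 2, and >99% satisfies >90%. Only the word minimum is loose.

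**The case for a change.** The strongest case for a correction is that the sentence cannot be checked. If uptake clusters by outlet much more than ACT targeting does, which is plausible when the incentive acts on the shopkeeper, power could fall below the stated figure. At 170 per outlet and an uptake ICC of 0.10 (assumed), 16 points has 73% power at 10% v 26% and 46% at 42% v 58%. A small denominator is also an unlikely source of the 89%. By section 6.1 the uptake denominator is everyone tested plus untested buyers of any antimalarial. Apart from clients who come with an outside test result, that takes in all the ACT buyers and more.

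Part of this stands. The label clashes with the section's own use of the word comparison, and the inputs are missing. It does not establish an error. Section 6.2 says power was calculated for the primary outcome but does not say it was calculated for nothing else. The sentence is introduced as an additional result and names its outcome. The ICC of 0.006 is stated for the primary outcome, so a larger value used for uptake would not contradict the text.

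**Conclusion.** No change to the plan is called for. The sentence has a loose label and unstated inputs, and a reader who knows that testing uptake is the major secondary outcome can still place it. The documents do not show the figure to be false. With the section's alpha and its ICC of 0.006, power for 16 points exceeds 89% once about 28 clients per outlet are analysable, over assumed baselines of 10% to 60%. This rests on borrowing the primary outcome's ICC. At 170 per outlet it would fail if the uptake ICC exceeded 0.036 to 0.067, depending on the baseline, and the plan gives no such value.

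Rewriting the sentence as Arm 4 versus Arm 3 at 14 points would replace one unverified reading with another. The sample of 8160 interviews is supported by Table 2 for all three Bonferroni-adjusted comparisons. Section 6.4 analyses uptake with the same GEE model whatever power is quoted. Neither the design nor any conclusion depends on this sentence.
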